8.2.2.3 Flu D-QIV humoral immunogenicity

Descriptive statistics, including 95% CIs, will be produced for the following Flu D-QIV humoral immunogenicity parameters for each of the 4 influenza vaccine strains by group and age categories (18-64, \geq 65 YOA). Summaries will be produced for the Flu D-QIV PPS.

- Anti-HI antibody titers against the 4 influenza strains included in Flu D-QIV expressed as GMTs with 95% CIs at pre-vaccination and at 1 month post Flu D-QIV (at Week 6 for FluD-QIVSeq, at Week 4 for FluD-QIVCoAd). GMT calculations will be performed by taking the anti-log of the mean of the log titer transformations. Anti-HI antibody titers will be displayed using reverse cumulative curves.
- SPR with exact 95% CIs at pre-vaccination and at 1 month post Flu D-QIV (at Week 6 for FluD-QIVSeq, at Week 4 for FluD-QIVCoAd). SPR is defined as the percentage of participants with a serum HI titer \geq 1:40.
- Seropositivity rates with exact 95% CIs at pre-vaccination and at 1 month post Flu D-QIV (at Week 6 for FluD-QIVSeq, at Week 4 for FluD-QIVCoAd). Seropositivity is defined as the percentage of participants whose antibody concentration is greater than or equal to the assay cut-off value (97 mIU/mL).

- MGI from pre-vaccination with 95% CIs at 1 month post Flu D-QIV (at Week 6 for FluD-QIVSeq, at Week 4 for FluD-QIVCoAd). MGI is defined as the geometric mean of the within participant ratios of the post-vaccination reciprocal HI titer to the pre-vaccination reciprocal HI titer.
- SCR with exact 95% CIs at 1 month post Flu D-QIV (at Week 6 for FluD-QIVSeq, at Week 4 for FluD-QIVCoAd). SCR is defined as the percentage of participants who have either a pre-vaccination titer $< 1:10$ and a post-vaccination titer $\geq 1:40$ or a pre-vaccination titer $\geq 1:10$ and at least a 4 fold increase in post-vaccination titer.

The assessment of SPR and SCR will also be performed by age categories (18-64, ≥ 65 YOA) descriptively based on the following CBER criteria:

- The lower limit of the 95% confidence interval for SPR should be $\geq 70\%$ in participants aged 18-64 YOA or $\geq 60\%$ in participants ≥ 65 YOA.
- The lower limit of the 95% confidence interval for SCR should be $\geq 40\%$ in participants aged 18-64 YOA or $\geq 30\%$ in participants ≥ 65 YOA.

At least one of the 4 strains must meet the criteria above for SPR and SCR to be considered as having met CBER criteria.

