
 To evaluate the humoral immunogenicity of Flu D-QIV. The assessment of SPR and SCR will be based on Center for Biologics Evaluation and Research's (CBER) criteria***. 	
 Anti-HI antibody titers against the 4 influenza strains included in Flu D-QIV expressed as GMTs with 95% CI at pre-vaccination and at 1 month post Flu D-QIV (at Week 6 for FluD-QIVSeq, at Week 4 for FluD-QIVCoAd). Seroprotection rate (SPR) with exact 95% CI at pre-vaccination and at 1 month post Flu D-QIV (at Week 6 for FluD-QIVSeq, at Week 4 for FluD-QIVCoAd), overall and by age category (18-64 and ≥65 YOA). Seropositivity rate with exact 95% CI at pre-vaccination and at 1 month post Flu D-QIV (at Week 6 for FluD-QIVSeq, at Week 4 for FluD-QIVCoAd). MGI with 95% CI from pre-vaccination at 1 month post Flu D-QIV (at Week 6 for FluD-QIVSeq, at Week 4 for FluD-QIVCoAd). SCR with exact 95% CI from pre-vaccination at 1 month post Flu D-QIV (at Week 6 for FluD-QIVSeq, at Week 4 for FluD-QIVCoAd), overall and by age category (18-64 and ≥65 YOA).

Objectives	Endpoints*

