8.1.2. Laboratory assays

Table 10 Laboratory assays

Assay Type	System	Component	Method	Laboratory
Humoral Immunity (Antibody Determination)	Serum	Anti-glycoprotein E Ab.IgG	ELISA	GSK
		Anti-S Protein Ab*	Multiplex Electrochemiluminescence assay**	PPD
		SARS-CoV-2 NA	Neutralization assay***	Nexelis
		A/Victoria/2570/2019	Hemagglutination Inhibition	Q2
		A/Tasmania/503/2020		Q2
		B/Washington/02/2019		Q2
		B/Phuket/3073/2013		Q2

Ab = antibody; ELISA = enzyme linked immunosorbent assay; NA = neutralizing antibody

*Responses to other antigens (e.g., anti-N and anti-RBD proteins) may be generated in addition to anti-S Protein.

**Other serological assays may be used to measure antibody responses

***Assay to be conducted on the virus strain in the booster dose

Table 11 Molecular biology

System	Component	Method	Unit	Laboratory
HZ lesion sample	Varicella Zoster Virus DNA	PCR	No unit	GSK
	Actin Gene DNA	PCR	No unit	GSK

HZ = herpes zoster; DNA = deoxyribonucleic acid; PCR = polymerase chain reaction

The addresses of clinical laboratories used for sample analysis are provided in a separate document accompanying this study protocol.

Exploratory testing on the vaccines and/or on the disease under study may be performed within the framework of the study (i.e., exploratory objective) if deemed necessary for accurate interpretation of the data. These assays may or may not be represented in the objectives/endpoints of the study protocol. Pending final assay evaluations and validations prior to study sample testing, the multiplex electrochemiluminescence testing for assessing mRNA-1273 booster immune responses as the primary endpoint may be replaced with a neutralization assay to measure SARS-CoV-2 neutralizing antibody titers in all study participants, and if not, the assessment of neutralizing antibody titers will be restricted to a sub-cohort of approximately 50 participants. In addition, the exploratory assessment of anti-gE humoral immunogenicity at 1 month post-dose 1 of HZ/su may be limited, based upon the nature of the responses observed following the second dose of HZ/su and scientific relevance.

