9.3.5.2. Descriptive immune endpoints

9.3.5.2.1. *Anti-gE humoral immunogenicity at pre-vaccination and post-dose 2 of HZ/su*

Descriptive statistics (including 95% CIs) of the following anti-gE humoral immunogenicity parameters will be provided by group and by age category (50-59, 60-69, ≥ 70 YOA). Analyses at 1 month post-dose 2 of HZ/su will use the HZ/su and mRNA-1273 PPS.

- VRR with exact 95% CI at 1 month post-dose 2 of HZ/su (at Week 14 for HZ/suSeq, at Week 12 for HZ/suCoAd)
 - The VRR for anti-gE post-dose 2 is defined as the percentage of participants who have at least:
 - A 4-fold increase in the post-dose anti-gE antibodies concentration as compared to the pre-vaccination anti-gE antibodies concentration, for participants who are seropositive at pre-vaccination, or,

- A 4-fold increase in the post-dose anti-gE antibodies concentrations as compared to the anti-gE antibodies cut-off value for seropositivity, for participants who are seronegative at pre-vaccination.

This will be summarized by participants who are seronegative at pre-vaccination, seropositive at pre-vaccination and overall status at pre-vaccination (seronegative or seropositive)

- Seropositivity rate with exact 95% CI at pre-vaccination (at Day 1 for HZ/suCoAd, at Week 2 for HZ/suSeq) and at 1 month post-dose 2 of HZ/su (at Week 14 for HZ/suSeq, at Week 12 for HZ/suCoAd). Seropositivity is defined as the percentage of participants whose antibody concentration is greater than or equal to the assay cut-off value (97 mIU/mL).
- Anti-gE antibody concentrations expressed as GMC with 95% CI at pre-vaccination (at Day 1 for HZ/suCoAd, at Week 2 for HZ/suSeq) and at 1 month post-dose 2 of HZ/su (at Week 14 for HZ/suSeq, at Week 12 for HZ/suCoAd). GMC calculations will be performed by taking the anti-log of the mean of the log concentration transformations. Anti-gE antibody concentrations will be displayed using reverse cumulative curves.
- MGI from pre-vaccination with 95% CI at 1 month post-dose 2 of HZ/su (at Week 14 for HZ/suSeq, at Week 12 for HZ/suCoAd).
- Descriptive statistics of fold increase from baseline for anti-gE antibody ELISA concentrations
- The distribution of the fold increase i.e. percentage of participants with a more than X-fold (e.g. >2, >4, >6,...-fold) increase along with 95% CI will be presented.

9.3.5.2.2. mRNA-1273 booster dose humoral immunogenicity

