Descriptive statistics (including 95% CIs) of the following mRNA-1273 booster immunogenicity parameters will be provided by group and by age category (50-59, 60-69, \geq 70 YOA for HZ/su and mRNA-1273 booster cohort, 18-64, \geq 65 YOA for Flu D-QIV and mRNA-1273 booster cohort). All summaries will be provided for the HZ/su and mRNA-1273 PPS and for the Flu D-QIV and mRNA-1273 PPS in the respective cohorts.

- Anti-S Protein antibody concentrations expressed as GMC with 95% CIs by group at pre-vaccination (Day 1) and 1 month post mRNA-1273 booster dose (at Week 4 for all groups including HZ/suSeq, HZ/suCoAd, FluD-QIVSeq, FluD-QIVCoAd and overall). The GMC calculations will be performed by taking the anti-log of the mean of the log concentration transformations. Anti-S protein antibody concentrations will be displayed using reverse cumulative curves.
- MGI with 95% CI at 1 month post mRNA-1273 booster dose (at Week 4 for all groups).

Pending final assay evaluations and validations prior to study specimen testing, anti-S protein may be replaced with SARS-CoV-2 neutralizing antibody titers in which case, GMTs will be used in the analysis described above.

9.3.5.2.3. *Flu D-QIV humoral immunogenicity*

Descriptive statistics, including 95% CIs, will be produced for the following Flu D-QIV humoral immunogenicity parameters for each of the 4 influenza vaccine strains by group and age categories (18-64, ≥ 65 YOA). Summaries will be produced for the Flu D-QIV and mRNA-1273 PPS.

- Anti-HI antibody titers against the 4 influenza strains included in Flu D-QIV expressed as GMTs with 95% CIs at pre-vaccination and at 1 month post Flu D-QIV (at Week 6 for FluD-QIVSeq, at Week 4 for FluD-QIVCoAd). GMT calculations will be performed by taking the anti-log of the mean of the log titer transformations. Anti-HI antibody titers will be displayed using reverse cumulative curves.

SPR with exact 95% CIs at pre-vaccination and at 1 month post Flu D-QIV (at Week 6 for FluD-QIVSeq, at Week 4 for FluD-QIVCoAd). SPR is defined as the percentage of participants with a serum HI titer $\geq 1:40$.

- Seropositivity rates with exact 95% CIs at pre-vaccination and at 1 month post Flu D-QIV (at Week 6 for FluD-QIVSeq, at Week 4 for FluD-QIVCoAd).

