8.2.2.1 Anti-gE humoral immunogenicity at pre-vaccination and post-dose 2 of HZ/su

Descriptive statistics (including 95% CIs) of the following anti-gE humoral immunogenicity parameters will be provided by group and by age strata (50-59, 60-69, \geq 70 YOA) at baseline and at 1 month post-dose 2 of HZ/su (at Week 14 for HZ/suSeq, at Week 12 for HZ/suCoAd) for the HZ/su PPS.

- VRR with exact 95% CI at 1 month post-dose 2 of HZ/su
 - The VRR for anti-gE post-dose 2 is defined as the percentage of participants who have at least:
 - 4-fold increase in the post-dose anti-gE antibody concentration as compared to the pre-vaccination anti-gE antibody concentration, for participants who are seropositive at pre-vaccination, or,
 - A 4-fold increase in the post-dose anti-gE antibody concentration as compared to the anti-gE antibody cut-off value of 97 mIU/mL for seropositivity, for participants who are seronegative at pre-vaccination.

This will be summarized by participants who are seronegative at pre-vaccination, seropositive at pre-vaccination and overall status at pre-vaccination (seronegative or seropositive).

- Seropositivity rate with exact 95% CI at pre-vaccination (at Day 1 for HZ/suCoAd, at Week 2 for HZ/suSeq) and at 1 month post-dose 2 of HZ/su (at Week 14 for HZ/suSeq, at Week 12 for HZ/suCoAd). Seropositivity is defined as the percentage of participants whose anti-gE antibody concentration is greater than or equal to the assay cutoff value (97 mIU/mL).
- Anti-gE antibody concentrations expressed as GMC with 95% CI at pre-vaccination (at Day 1 for HZ/suCoAd, at Week 2 for HZ/suSeq) and at 1 month post-dose 2 of HZ/su (at Week 14 for HZ/suSeq, at Week 12 for HZ/suCoAd). GMC calculations will be performed by taking the anti-log of the mean of the log concentration transformations. Anti-gE antibody concentrations at all time points (pre, Dose 1 and Dose 2) will be displayed using reverse cumulative curves.
- MGI in anti-gE antibody from pre-vaccination with 95% CI at 1 month post-dose 2 of HZ/su (at Week 14 for HZ/suSeq, at Week 12 for HZ/suCoAd).

- Descriptive statistics of fold increase from baseline for anti-gE antibody enzyme linked immunosorbent assay (ELISA) concentrations.
- The distribution of the fold increase in anti-gE antibody ELISA concentrations i.e. percentage of participants with a more than X-fold (e.g. >2, >4, >6,...-fold) increase along with 95% CI will be presented.

8.2.2.2 mRNA-1273 booster dose humoral immunogenicity

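### SAP 8.2.2.3 defines influenza HI seropositivity with the anti-gE ELISA cut-off and unit (97 mIU/mL), so this descriptive secondary endpoint cannot be computed as written

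*SAP*

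**What the plan says.** HI seropositivity is a listed secondary endpoint for Flu D-QIV. Protocol Section 3 (Table 7) has "Seropositivity rate with exact 95% CI at pre-vaccination and at 1 month post Flu D-QIV", and SAP 2.2 lists the same rate. Protocol 9.3.5.2.3 repeats it in the analysis section: "Seropositivity rates with exact 95% CIs at pre-vaccination and at 1 month post Flu D-QIV". None of these three places gives a cut-off.

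The only definition is in SAP 8.2.2.3: "Seropositivity is defined as the percentage of participants whose antibody concentration is greater than or equal to the assay cut-off value (97 mIU/mL". This is current text in the amended SAP. The SAP of 3 December 2021 carried the same sentence, and the amendment left it unchanged.

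The other parameters in SAP 8.2.2.3 are on the titer scale. For seroprotection, "SPR is defined as the percentage of participants with a serum HI titer" of at least 1:40. MGI is built from the ratio of the "post-vaccination reciprocal HI titer to the pre-vaccination reciprocal HI titer". Seroconversion uses titers of 1:10 and 1:40 and a 4-fold rise.

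**The concern.** The number and the unit both come from the zoster assay. SAP 8.2.2.1 refers to the "anti-gE antibody cut-off value of 97 mIU/mL for seropositivity", and protocol 9.3.5.2.1, the anti-gE section, counts participants "whose antibody concentration is greater than or equal to the assay cut-off value (97 mIU/mL". The influenza sentence in the SAP matches that protocol sentence word for word, which points to a definition copied from one antigen to the other.

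At stake is whether a listed secondary endpoint has a usable prespecified definition. If the sentence is followed, the programmer must either stop because the unit does not match, or apply 97 to a scale on which it has no stated meaning. If it is ignored, the programmer must choose a cut-off that the SAP should have supplied.

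**Working it through.** The cut-off is a stated constant, so there is no plan figure to reproduce. The check sets the places side by side, tests the rule on the HI scale and counts its reach.

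**1. Which assay owns 97 mIU/mL.**
- Protocol 9.3.5.2.1: seropositivity cut-off, under the anti-gE heading.
- SAP 8.2.2.1: named as the anti-gE cut-off, in the vaccine response definition and again for seropositivity.
- SAP 8.2.2.3: the same value, under the influenza heading, with no assay named.
- Protocol 8.1.2 (Table 10): anti-gE is measured by ELISA; the four influenza strains are measured by "Hemagglutination Inhibition".

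Outside the influenza sentence, both documents use 97 mIU/mL only for anti-gE.

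**2. Whether another definition fills the gap.**
- Protocol Table 7, protocol 9.3.5.2.3 and SAP 2.2 list the rate without a cut-off.
- SAP Section 4 says how to handle values below the LLOQ but gives no HI LLOQ.
- The seroconversion definition splits pre-vaccination titers at 1:10. Neither document calls that the seropositivity cut-off.
- No conversion from HI titer to mIU/mL is given.

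So no other text rescues the definition.

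**3. What happens if the unit is dropped.** Let T be the reciprocal HI titer.
- Seroprotection: T ≥ 40. Seropositivity under the rule: T ≥ 97.
- Because 97 > 40, every T ≥ 97 also satisfies T ≥ 40. Hence rate(T ≥ 97) ≤ rate(T ≥ 40) = SPR for any titer distribution, with equality only if nobody has 40 ≤ T < 97.
- Illustration, assuming a two-fold series 10, 20, 40, 80, 160 (the documents do not state the series): the first qualifying titer is 160, so participants at 40 and 80 are seroprotected but classed as seronegative.

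The ordering needs no assumption. The size of the gap cannot be derived, because the documents give no HI titer distribution.

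**4. Reach.**
- Overall: 4 strains × 2 groups × 2 timepoints = 16 rates.
- Flu cohort subgroup levels in SAP 4.4: age 2 + gender 2 + race 6 + ethnicity 2 = 12.
- SAP Section 8 repeats secondary immunogenicity summaries for all these subgroups, on the applicable PPS and the Exposed Set: 16 × (1 + 12) = 208 per set, and 208 × 2 = 416 in all.

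The 416 is an upper count, since small race levels may be empty. It measures how often the definition is used, not bias.

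**The case against.** The best defence is that the operative words are the assay cut-off, with 97 mIU/mL only a parenthetical gloss. A programmer given HI titers would notice the wrong unit, query it and use the HI assay's own cut-off, in which case the error has no numerical effect. The comparison with seroprotection then never arises, because it requires someone to strip the unit, and nothing shows that this was intended or done. The 1:10 split in the seroconversion definition also offers a natural candidate.

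Part of this stands. The wrong number may never have reached the programs; the table shells are not provided, so this cannot be told. The 416 count adds nothing to the severity.

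The definition itself is not saved. Setting the parenthesis aside leaves no value at all, because the HI cut-off appears nowhere. The 1:10 threshold is plausible but is not labelled as the seropositivity cut-off, and adopting it without confirmation would be a guess. Whoever resolves the mismatch at the programming stage would be defining the endpoint.

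**Conclusion.** The concern holds. SAP 8.2.2.3 attaches another assay's threshold and unit to a listed secondary endpoint, and neither document supplies an HI cut-off to use instead. Read literally, the rule cannot be applied to HI titers; with the unit dropped, it puts seropositivity at or below seroprotection.

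The severity is minor. The effect is confined to the descriptive HI seropositivity rates: 16 overall, plus their repeats. Hypotheses 1 to 5, the GMT, SPR, SCR and MGI summaries, the CBER criteria, the power calculations and the anti-gE endpoints use other definitions and are unaffected. The conclusion rests on the text alone. The numerical size of any misclassification is unknown and could be zero if the HI assay's own cut-off was used in programming.

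**What to change.** In SAP 8.2.2.3, define HI seropositivity as the percentage of participants whose HI titer is at or above the HI assay cut-off, stated as a reciprocal titer confirmed by the HI testing laboratory. Word it to allow strain-specific values if the laboratory does not use one cut-off for all four strains. Keep 97 mIU/mL for anti-gE only. Do not adopt 1:10 or any other value without that confirmation.

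The cost is one query to the laboratory, one corrected SAP sentence and a check of the matching programming constant (or one per strain). SAP Section 1 says the amendment is finalized before final database lock, which is the natural point for the correction. If lock has passed, record the cut-off actually used, and the reason, in the Clinical Study Report.

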8.3. Exploratory Immunogenicity Endpoints

Anti-gE humoral immunogenicity at post-dose 1 of HZ/su:

- Anti-gE antibody testing post-dose 1 may be limited, based upon the nature of the responses observed following the second dose of HZ/su and scientific relevance. Similar descriptive statistics will be presented for these results at 1 month post-dose 1 of HZ/su as described in Section 8.2.2.1. The summary of this data will use HZ/su PPS. This summary will not be in the initial study report as it will only be conducted once the results of study report are reviewed and if needed, additional lab results obtained.

Neutralizing antibodies for SARS-CoV-2 (assuming if not assessed as a primary endpoint in all participants):

- GMT with 95% CI of SARS-CoV-2 neutralizing antibody concentrations in a sub-cohort of participants in each study group (HZ/suSeq, HZ/suCoAd, FluD-QIVSeq, FluD-QIVCoAd and overall) at pre-vaccination and 1 month post mRNA-1273 booster (at Week 4 for all groups). The sub-cohort (approximately 50 evaluable participants) will be selected post-hoc, based on other observed immune assay results. Summaries will be produced for the mRNA-1273 PPS per cohort.

Descriptive humoral immune responses to vaccination and/or SARS-CoV-2 infection for anti-RBD protein:

- GMCs with 95% CI of anti-RBD protein antibodies at pre-vaccination and at 1 month post mRNA-1273 booster (at Week 4 for all study groups [HZ/suSeq, HZ/suCoAd, FluD-QIVSeq, FluD-QIVCoAd and overall]). Summaries will be produced for the mRNA-1273 PPS per cohort.

Descriptive humoral immune responses to SARS-CoV-2 infection for anti-N:

- Anti-N seroconversion rate with exact 95% CI from pre-vaccination to 1 month post mRNA-1273 booster dose (at Week 4 for all study groups). Seroconversion is defined as a participant who is seronegative at baseline and seropositive postvaccination OR for a participant seropositive at baseline, a 4-fold or more increase post-vaccination. Summaries will be produced for the mRNA-1273 PPS per cohort.

9. Safety Analysis

Safety analysis includes solicited AEs, unsolicited AEs, SAEs, pIMDs, AESIs, COVID-19 cases, HZ episodes/cases, pregnancy tests and pregnancy events/outcomes. The safety endpoints will be summarized for each cohort on the HZ/su and mRNA-1273 Exposed Set and on the Flu D-QIV and mRNA-1273 Exposed Set, respectively. PIMDs, and HZ episodes/cases will be summarized on the HZ/su and mRNA-1273 Exposed Set only. All the safety analyses under the secondary objective are descriptive. Subgroup analyses by age strata (as applicable to each study cohort), gender, race, and ethnicity as defined in Section 4.4 will be performed on select AE summaries.

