8.1.3. Immunological read-outs

Table 12 Immunological read-outs

Study Group	Number of participants	Visit 1 Day 1	Visit 2	Visit 3	Visit 4	Visit 6
HZ/suSeq	273	SARS-CoV-2 Neutralizing Ab* Anti-S Protein IgG Ab**	Anti-gE Ab	SARS-CoV-2 Neutralizing Ab* Anti S Protein IgG Ab**	Anti-gE Ab	Anti-gE Ab
HZ/suCoAd	273	SARS-CoV-2 Neutralizing Ab* Anti-S Protein IgG Ab** Anti-gE Ab	SARS-CoV-2 Neutralizing Ab * Anti S Protein IgG Ab** Anti-gE Ab	-	Anti-gE Ab	-
FluD-QIVSeq	500	SARS-CoV-2 Neutralizing Ab* Anti-S Protein IgG Ab**	HI Ab	SARS-CoV-2 Neutralizing Ab* Anti S Protein IgG Ab**	HI Ab	-
FluD-QIVCoAd	500	SARS-CoV-2 Neutralizing Ab* Anti-S Protein IgG Ab** HI Ab	SARS-CoV-2 Neutralizing Ab* Anti S Protein IgG Ab** HI Ab	-	-	-

Ab = antibodies; IgG = immunoglobulin G

*Samples may be tested on a sub-cohort (approximately 50 evaluable participants) post-hoc, based on other observed immune assay results or in all study participants if selected as a primary endpoint

**Responses to other antigens (e.g., anti-N and anti-RBD proteins) may be generated in addition to anti-Spike Protein

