9.3.7. Exploratory endpoints analyses

Anti-gE humoral immunogenicity at post-dose 1 of HZ/su:

Anti-gE antibody testing post-dose 1 may be limited, based upon the nature of the responses observed following the second dose of HZ/su and scientific relevance. Similar descriptive statistics will be presented for these results at 1 month post-dose 1 of HZ/su as described in Section 9.3.5.2.1.

Confirmed HZ cases (for HZ/su and mRNA-1273 booster cohort only):

- Number and percentage of participants reporting clinically confirmed HZ cases by PCR from first vaccination up to study end will be summarized for all study groups (HZ/suSeq, HZ/suCoAd, and overall).

Neutralizing antibodies (assuming if not assessed as a primary endpoint in all participants):

- GMT with 95% CI of SARS-CoV-2 neutralizing antibody concentrations in a sub-cohort of participants in each study group (HZ/suSeq, HZ/suCoAd, FluD-QIVSeq, FluD-QIVCoAd and overall) at pre-vaccination and 1 month post mRNA-1273 booster (at Week 4 for all groups). The sub-cohort (approximately 50 evaluable participants) will be selected post-hoc, based on other observed immune assay results.

Descriptive humoral immune responses to vaccination and/or SARS-CoV-2 infection:

- GMCs with 95% CI of anti-RBD protein antibodies at pre-vaccination and at 1 month post mRNA-1273 booster (at Week 4 for all study groups [HZ/suSeq, HZ/suCoAd, FluD-QIVSeq, FluD-QIVCoAd and overall]).

Descriptive humoral immune responses to SARS-CoV-2 infection:

- Anti-N seroconversion rate with exact 95% CI from pre-vaccination to 1 month post mRNA-1273 booster dose (at Week 4 for all study groups). Seroconversion is defined as a participant who is seronegative at baseline and seropositive post-vaccination OR for a participant seropositive at baseline, a 4-fold or more increase post-vaccination.

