9.5. Sample size determination

Assumptions used for the sample size calculations come from data available from prior studies ZOSTER-004 (117036), ZOSTER-042 (116887), ZOSTER-035 (116889), ZOSTER-048 (201198), ZOSTER-059 (204487), FLU D-QIV-008 (114269), FLU D-QIV-010 PRI (117276), and EXPLO-CRD-004, as well as preliminary mRNA-1273 Phase I and Phase II data [Jackson, 2020; Chu, 2021].

After final assay evaluations and validations, should the primary mRNA-1273 endpoint be replaced by SARS-CoV-2 neutralizing antibody titers, the same assumptions will be made since the standard deviation used for calculations was at the upper range of what has been observed for both endpoints; thus, the sample sizes presented below will remain for each cohort.

The type I error to be maintained is 0.025 (one-sided) for each study cohort (HZ/su and mRNA-1273 booster, Flu D-QIV and mRNA-1273 booster). Study success will be evaluated separately for each cohort. For the HZ/su and mRNA-1273 booster cohort, non-inferiority must be achieved for both hypothesis 1 and hypothesis 2. For the Flu D-QIV and mRNA-1273 booster cohort, success must be achieved for both hypothesis 3 and hypothesis 4.

A total of 1546 participants will need to be enrolled and randomized between the 2 cohorts.

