Enrolled participant:	“Enrolled” means a participant’s agreement to participate in a clinical study following completion of the informed consent process.
Essential documents:	Documents which individually and collectively permit evaluation of the conduct of a study and the quality of the data produced.
eTrack:	GSK’s tracking tool for clinical studies.

Evaluable:	Meeting all eligibility criteria, complying with the procedures defined in the protocol, and, therefore, included in the per protocol analysis.
Immunological correlate of protection:	A correlate of risk that has been validated to predict a certain level of protection from the targeted endpoint.
Intercurrent medical condition	A condition that has the capability of altering the immune response to the study intervention or is confirmed to have an alteration of the participant's initial immune status.
Intervention:	Term used throughout the clinical study to denote a set of investigational product(s) or marketed product(s) or placebo intended to be administered to a participant.
Invasive medical device:	A device which, in whole or in part, penetrates inside the body, either through a body orifice or through the surface of the body
Investigational vaccine/product:	A pharmaceutical form of an active ingredient being tested in a clinical study, including a product with a marketing authorization when used in a way different from the approved form, or when used for an unapproved indication, or when used to gain further information about an approved use.
Investigator:	A person responsible for the conduct of the clinical study at a study center. If a study is conducted by a team of individuals at a study center, the investigator is the responsible leader of the team and may be called the principal investigator. The investigator can delegate study-related duties and functions conducted at the study center to qualified individual or party to perform those study-related duties and functions.
Interactive Voice/Web Response System:	The software that enables the randomizing of participants into clinical trials and allocation of the study product to them in a blinded fashion. This technology allows study centers to interact with a database by pressing keypad buttons on a phone and following voice or online prompts in order to enter in information.

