Descriptive statistics (including 95% CIs) of the following mRNA-1273 booster immunogenicity parameters will be provided by group and by age strata (50-59, 60- 69, \geq 70 YOA for HZ/su and mRNA-1273 booster cohort; 18-64 and \geq 65 YOA for Flu DQIV and mRNA-1273 booster cohort). All summaries will be provided for the mRNA-1273 PPS by cohort.

- Anti-S Protein antibody concentrations expressed as GMC with 95% CIs by group at pre-vaccination (Day 1) and 1 month post mRNA-1273 booster dose (at Week 4 for all groups including HZ/suSeq, HZ/suCoAd, FluD-QIVSeq, FluD-QIVCoAd and overall). The GMC calculations will be performed by taking the anti-log of the mean of the log concentration transformations. Anti-S protein antibody concentrations will be displayed using reverse cumulative curves.
- MGI with 95% CI at 1 month post mRNA-1273 booster dose (at Week 4 for all groups).

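### The exploratory neutralizing-antibody sub-cohort is chosen after other immune results are seen, with no stated rule, per-group number or weights, so its GMTs and CIs cannot be taken to represent the study groups

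*SAP*

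**What the plan says.** The sub-cohort applies only if neutralizing antibody has not replaced anti-S as the primary mRNA-1273 endpoint; SAP 4.1 and 8.1.1 keep that replacement open.

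- **Selection.** SAP 8.3: "The sub-cohort (approximately 50 evaluable participants) will be selected post-hoc, based on other observed immune assay results". Protocol 9.3.7 has the same rule: the sub-cohort "will be selected post-hoc, based on other observed immune assay results". The footnote to Protocol Table 12 (8.1.3) is looser: "Samples may be tested on a sub-cohort (approximately 50 evaluable participants) post-hoc, based on other observed immune assay results".
- **What is reported.** SAP 8.3 plans "GMT with 95% CI of SARS-CoV-2 neutralizing antibody concentrations in a sub-cohort of participants in each study group", before vaccination and at Week 4, and overall. The summaries are assigned to the mRNA-1273 PPS of each cohort.
- **Size.** Protocol 8.1.2 says that "the assessment of neutralizing antibody titers will be restricted to a sub-cohort of approximately 50 participants", which reads as a study total. The SAP 8.3 wording could mean about 50 in each group.
- **Who is eligible.** The protocol glossary (10.5.2) defines evaluable participants as those meeting eligibility and "complying with the procedures defined in the protocol, and, therefore, included in the per protocol analysis". The introduction to SAP Section 8 nevertheless repeats all exploratory immunogenicity summaries on the Exposed Set.
- **Knowledge of allocation.** Protocol 6.3.4 states that the study is open-label and that all parties know the group once a participant is randomized.

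**The concern.** An ordinary GMT with a 95% CI describes a study group only if the tested participants were chosen in a way that does not depend on their response, or if the dependence is known and corrected. Here the plan says that selection follows other immune results, and it supplies nothing with which to correct for that. Anti-S is an obvious candidate for the selecting assay, and it may well be correlated with neutralization. Nothing requires the same rule in the sequential and co-administration groups, although the results are displayed by group and allocation is known.

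What is at stake is the reading of one exploratory table. If anti-S stays primary, these are the only neutralizing-antibody summaries planned, and they would carry a PPS label that suggests they stand for the whole group.

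**Working it through.** **Is there a plan figure to reproduce?** The figure of about 50 has no derivation. The only planning input used below is the log10 SD of 0.45 for the mRNA-1273 endpoint (SAP Table 3). Protocol 9.5 extends it to neutralizing titers, saying that "the standard deviation used for calculations was at the upper range of what has been observed for both endpoints". As a check that 0.45 is the value behind the planned power: difference = log10(1.5) − log10(1.1) = 0.1347; standard error = 0.45 × √(2/245) = 0.0407; non-centrality = 3.31; one-sided alpha 0.025. Power is 91.1% by the non-central t, matching the 91.1% stated.

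**What the size ambiguity means.** The 95% CI of one group's GMT is the estimate multiplied and divided by 10^(t × 0.45/√n), under a random draw and an even split:

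| Reading of 50 | n per group | Participants tested | CI factor |
|---|---|---|---|
| Total | 12 to 13 | 50 | 1.93 to 1.87 |
| Per cohort | 25 | 100 | 1.53 |
| Per study group | 50 | 200 | 1.34 |

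**What selection could do.** The documents give neither the rule nor the correlation ρ between neutralization and the selecting assay, so both are assumed. With bivariate-normal log titers, the log10 shift of the mean is ρ × 0.45 × E[Z | selected]. For one half of the distribution, E[Z | selected] = ±√(2/π) = ±0.798. At ρ = 0.6 the shift is ±0.6 × 0.45 × 0.798 = ±0.215, so the GMT is multiplied by 10^−0.215 = 0.61 or 10^0.215 = 1.64.

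Coverage of the study-group mean by a nominal 95% t-interval was simulated with 245 evaluable per group and 6,000 runs per cell. Lower-half selection, against a random draw:

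| ρ | GMT factor, lower half | GMT factor, upper half | Coverage, lower half, n=50 | Coverage, lower half, n=12 | Coverage, random, n=50 |
|---|---|---|---|---|---|
| 0 | 1.00 | 1.00 | about 95% | about 95% | about 95% |
| 0.3 | 0.78 | 1.28 | about 60% | about 88% | about 95% |
| 0.6 | 0.61 | 1.64 | about 3.5% | about 60% | about 95% |
| 0.9 | 0.48 | 2.10 | 0% | 7 to 9% | about 95% |

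Symmetric rules (the middle half, both outer quarters, or equal numbers from each quarter) leave the GMT factor at 0.99 to 1.01. Interval coverage is then off nominal in either direction, from about 89% to nearly 100%. Starting from 450 evaluable per group changes these results by no more than about 3 points.

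**What known probabilities recover.** Sampling 25/10/10/5 from the four quarters of the selecting assay gives an unweighted GMT factor of about 0.74 at ρ = 0.6. Weighting back to the quarters gives 1.00.

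**The case against.** The strongest reply is that the plan promises very little here. The endpoint is exploratory, descriptive and conditional, and is openly defined as titers in a sub-cohort. No test, between-group ratio or success criterion uses it. Assigning the summary to the mRNA-1273 PPS may mean only that those tested are PPS members. The booster response is also described without it: for anti-S, SAP 8.2.2.2 says "All summaries will be provided for the mRNA-1273 PPS by cohort", and anti-RBD in SAP 8.3 is not restricted to a subset. Choosing samples on earlier results can be legitimate in exploratory work. Most of this stands, and it sets the severity.

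Two parts do not remove the point. The Table 12 footnote could mean that only the decision to test depends on results, but SAP 8.3 and Protocol 9.3.7 say that the sub-cohort itself is selected on them. Calling the group a sub-cohort does not tell a reader how it differs from the study group, and a CI invites generalization.

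A reader might infer that these GMTs will be biased, or that samples will be picked to favour co-administration. The documents do not support that. They state no direction or threshold, and a random draw, a symmetric rule or an unrelated assay would leave the GMT unbiased. The large factors above come from assumed one-sided rules. A reader might also infer that the non-inferiority conclusions are affected. They are not: if neutralizing titers became primary, all participants would be tested and this sub-cohort would not be used.

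**Conclusion.** The point holds as a minor one. Because the selecting assay, rule, per-group number and weights are unstated, the sub-cohort GMTs and CIs cannot be taken to represent the study groups. Whether they would be biased, in which direction and by how much cannot be derived from the documents. The factors of 0.61 and 1.64 rest on an assumed correlation of 0.6, one-sided half selection, normal log titers and an SD that the protocol puts at the upper range, so they lean high. The unclear size on its own would be only a missing detail; it matters here because it changes the precision of a group GMT from a factor of about 1.9 to 1.34. Hypotheses 1 to 5, their power and the full-set anti-S and anti-RBD summaries are unaffected.

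**What to change.** In SAP 8.3, replace the selection sentence with: *The sub-cohort will be a computer-generated random sample of the mRNA-1273 PPS, stratified by study group, drawn without reference to immunogenicity results; n = [state] per study group.*

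If coverage of the anti-S range is wanted, sample with known probabilities within anti-S strata, with the same rule in every group, and report weighted GMTs with CIs that allow for the sampling.

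With either option:

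- State that the Exposed Set repeat in the introduction to SAP Section 8 does not apply to this sub-cohort, or uses the same participants.
- Align Protocol 9.3.7 and the Table 12 footnote, or record the departure in SAP Section 12.
- If participants have already been selected on results, report the rule used and label the GMTs as describing the tested participants only.

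The cost is a few lines of text and a random draw from stored samples. The number of assays is unchanged if 50 keeps its intended meaning; if 50 was a total and 50 per group is preferred, 200 participants are tested instead of 50. The real loss is the freedom to choose samples after seeing other results.
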